12. PUBLICATION, REPORTS AND DATA SHARING

Publication of the main reports from the study will be in the name of the ENCHANTED2 Investigators. Full editorial control will reside with a Writing Committee approved by the SC.

Investigators have the right to publish or present the results of the study. However, as this is a multi-site academic study, investigators agree not to publish or publicly present any interim results of the study without the prior written consent of the SC. Investigators further agree to provide the SC at least 30 days prior to submission for publication or presentation, review of copies of abstracts or manuscripts (including without limitation, text and PowerPoint presentation slides and any other texts of transmissions or media presentations) that report any results of the study.

The SC shall have the right to review and comment with respect to publications, abstracts, slides, and manuscripts. The SC also have the right to review and comment on the data analysis and presentation with regard to the accuracy of the information, the protection of the rights of individuals, and to ensure that the presentation is fairly balanced and in compliance with appropriate regulations.

If the parties disagree concerning the appropriateness of the data analysis and presentation, and/or confidentiality, the particular investigator(s) will agree to meet with members of the SC at the clinical site or as otherwise agreed, prior to submission for publication, for the purpose of making good faith efforts to discuss and resolve any disagreements.

Writing Committees will be formed from members of the various committees, statisticians, research fellows and investigators. They will prepare the main reports of the study to be published in the name of “ENCHANTED2 Investigators” with credit assigned to the collaborating investigators and other research staff. Presentations of the study findings will be made at national and international meetings concerned with the management of stroke, cardiovascular disease, and hypertension.

Authors of publications must meet the International Committee of Medical Journal Editors (ICMJE) guidelines for authorship that follow:

1 Authors must make substantial contributions to the conception and design of the trial, acquisition of data, or analysis of data and interpretation of results;

2 Authors must draft the publication or, during draft review, provide contributions (data analysis, interpretation, or other important intellectual content) leading to significant revision of the manuscript with agreement by the other authors;

3 Authors must provide approval of the final draft version of the manuscript before it is submitted to the journal for publication.

All contributors who do not meet the 3 criteria for authorship should be listed in an acknowledgments section within the publication, if allowed by the journal, per ICMJE guidelines for acknowledgement.

At the completion of the study, requests for secondary analysis will be in accordance with a defined protocol from an experience research group with an agreed analysis plan with The George Institute. In addition, data will be shared with other investigators on the study, and investigators from other institutions around the word, according to a strict data sharing agreement.

Data sharing will be available from 12 months after publication of the main results. The consent form will include information as to the purpose of this activity. Investigators are to make a formal request for data sharing through the Research Office of TGI, CHINA and get approval from the SC.

13. ORGANISATION

Central coordination is from TGI, CHINA, and the study will be overseen by an International SC comprised of world experts in the fields of stroke, hypertension, neurology, geriatrics, cardiovascular epidemiology and clinical trials. The CCC will also be supported by key grant holders and regional experts in the OC. The CCC communicates with regional committees and approximately 80-100 participating hospitals in China in the first instance, and up to 50 sites outside of China depending on funding. Sites will be administratively tied through a structure designed to enhance effective communication and collaboration as well as monitor and maintain operations through adherence to a common protocol.

13.2 Central Coordinating Centre (CCC)

The CCC is at TGI, CHINA

Responsibilities: Day to day management of the study, data and project management, committee coordination, assistance with ethics committee applications, protocol and procedures training for participating centres, initiation visits to participating centres, monitoring of data quality and adherence to applicable guidelines and regulations, preparation of study data for analysis and publication.

13.3 RCC

Responsibilities: Provide advice to the CCC on regional issues relevant to the set up and management of the study. In conjunction with the CCC, provide assistance and support and monitor study progress at regional participating centres, including data quality and adherence to the study protocol.

13.4 Imaging Adjudication Committee (Core Lab/Brain Imaging Analysis)

Responsibilities: To measure haemorrhagic complications (hematoma volume) and ischemia/infarction on all de-identified and blinded brain imaging scans (blinded by allocation group and timing of scan).

13.5 Clinical Endpoints Committee

Responsibilities: Review blinded study outcomes to ensure endpoints meet the consistent diagnostic criteria in line with pre-determined criteria.

13.6 Data Safety Monitoring Board (DSMB)

Responsibilities: Review the safety, ethics and outcomes of the study.

13.7 Participating Centres

Neurology Wards / Neurosurgery Departments / Acute Stroke Units

Responsibilities: Overall management of study at own hospital in line with the study protocol; study nurse recruitment and orientation; protocol education of colleagues, patient recruitment, data collection and data transfer to the CCC, data query resolutions, liaison with local Hospital Research Ethics Committee/Institutional Review Board, adherence to local ethics guidelines and reporting requirements, adverse event reporting to local Hospital Research Ethics Committee/Institutional Review Board and to the CCC in accordance with protocol.

14. FUNDING

Funding for the study is part of a consortium, with research grants held by TGI, CHINA and Shanghai Hospital. This study has received initial funding from a Program Grant from the National Health and Medical Research Council (NHMRC) of Australia (APP1149987), China National Health Commission Stroke Prevention Committee “China Stroke Prevention and Intervention Project” (GN-2020 R0008), and grants from Shanghai Hospital (including “National Clinical Key Specialist Construction Project’ 2016). This study also receives funding support from Takeda China.

15. TIMELINES

Milestones for main study	2019	2020	2021	2022	2023
Protocol design and materials development	→				
Sign contract with investigators	→				
Set-up of regional centres	→				
Ethics applications	→				
Training sites	→				
Commence recruitment and intervention	→				
Outcomes assessment	→				
Close out				→	
Analysis and Results				→	
Presentation / publication of main result					A

17. APPENDIX

Appendix 1 - BP management protocol

Appendix 1A - BP protocol for centres with Urapidil (China)

Intensive BP lowering group	TREATMENT PROTOCOL
INITIAL therapy	
BP Target	SBP <120mmHg achieved within 1 hour after randomisation
Monitoring	
 Continuous HR monitoring Record BP/HR q 5 mins during active treatment, then q 15 min for first hour, q 30 min for next 5 hours and then hourly to 24 h
Urapidil (IV)	
 If SBP \geq 120 mmHg and HR >55 bpm, repeat 10-25 mg IV bolus q5 mins until target SBP reached (<120mmHg) or HR <55 bpm If HR increases by >15 bpm or is >90 bpm, add IV beta blocker
Hydralazine (IV)	
 Hydralazine test dose: 5 mg IV bolus over 1 minute If SBP \geq 120 mmHg, repeat 5 mg IV bolus in 5 minutes If SBP still \geq 120mmHg, give 10 mg IV bolus q 5 mins until target SBP reached Increase to 20 mg bolus if required Maximum hydralazine dose = 240mg
Glyceryl Trinitrate (topical)	
If BP persistently \geq 120 mmHg:
 
 ADD topical glyceryl trinitrate (paste or patch) at a rate of 5-10 mg/24 hour 
(\approx 200-400 μg/hour). NB: also known as topical nitroglycerin

Continuous IV Infusions (requires ICU admission)	
If BP persistently \geq 120 mmHg:
 
 Urapidil infusion 5-30 mg/hour If target still not reached ADD infusion of hydralazine 50-150 μg/min OR glyceryl trinitrate 1-100 μg/Kg/min
MAINTENANCE therapy	
BP Target	Maintenance of SBP 100-120 mmHg
Monitoring	Once SBP is under target (confirmed by 4 readings 15 minutes apart): 
 Record BP/HR q 30 minutes for 5 hours and then q 1 h for 18 h
IV treatment prn	
If SBP exceeds 120mmHg at any point:
 
 Give Urapidil (10-25 mg) and/or hydralazine (10-20 mg) boluses. BP and HR should then be recorded 5 and 15 minutes later If SBP is 100-120mmHg, Urapidil 10-25 mg (dose dependent on initial response) should be administered q 6 hours for the first 24 hours after symptom onset (total of 3 doses) If SBP \leq 100 mmHg, cease therapy If HR increases by >15 bpm or is >90 bpm, add IV beta blocker Note: urapidil and hydralazine may be used together during the maintenance phase

Oral treatment

Start treatment by 24 hours (use nasogastric if required)

- If not contraindicated and no other drug is specifically indicated, start combination therapy of ACEI + diuretics \pm previous antihypertensives

Note: Monoamine oxidase inhibitors are not recommended with this BP lowering agent and phosphodiesterase inhibitors must not be used with GTN.

Key to abbreviations: ACEI – Angiotensin converting enzyme inhibitor; BP – blood pressure; bpm – beats per minute; HR – heart rate; ICU – intensive care unit; q – every; prn – as required; $\mu\text{g}/\text{Kg}/\text{min}$ – micrograms per kilogram per minute; $\mu\text{g}/\text{min}$ – micrograms per minute.

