6.7 Treatments Allocation

Attending clinicians are required to consider their level of clinical uncertainty over the balance of potential benefits and risks pertaining to the level of BP control in each particular patient. Investigators are encouraged to adhere to study protocols, provide active care, but are free to modify a patient's treatment as required according to clinical judgment.

Intensive BP lowering group

The aim is to achieve a systolic BP level of <120mmHg within 1 hour after randomisation and to maintain this BP level for the next 72 hours (or until hospital discharge or death if this should occur earlier). A standardised intravenous (i.v.) BP lowering regimen using locally available and approved i.v. BP lowering agents will be used, commenced immediately after randomisation in either the catheter lab or a high dependency area (e.g. acute stroke or neurointensive care unit) as is usual for patients receiving MT.

BP lowering will be titrated by repeat i.v. bolus or infusion, with a systolic BP of 100 mmHg being the safety threshold for cessation of therapy. It is anticipated that i.v. agents will be required for at least the first several hours in most cases but the timing of switch to oral BP lowering agents will be at the discretion of the responsible clinician according to BP control and patient status. It is also expected that i.v. therapy will continue to be required during the initiation of oral antihypertensive therapy, to maintain the systolic BP levels 100-120 mmHg.

When administering BP lowering treatment, care is required to ensure that severe hypotension is avoided in patients by checking first for potential dehydration and providing intravenous fluids.

Since the study seeks to address the impact of BP lowering and not a specific agent, and to ensure the trial result is maximally generalizable to existing routine practice, some flexibility is allowed in the use of locally available i.v. agents (e.g. urapidil, hydralazine, metoprolol, clevipipine), but all other aspects treatment are standardized across sites. Patients on prior oral BP lowering agents should have this continued if possible and antihypertensive therapy prescribed when patients are clinically stable as per guidelines for secondary stroke prevention. Investigators are encouraged to adhere to study protocols, provide active care, but are free to modify a patient's treatment as required according to clinical judgment.

I.v. treatment protocol

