Appendix 1B - BP protocol for centres with Phentolamine (China)

Intensive BP lowering group

TREATMENT PROTOCOL

INITIAL therapy

BP Target	SBP < 120 mmHg reached within 1 hours after randomisation
Monitoring	
 Continuous HR monitoring Record BP/HR q 5 mins during active treatment, then q 15 min for first hour, q 30 min for next 5 hours and then hourly to 24 h
Phentolamine (IV)	
 If SBP \geq120 mmHg and HR >55 bpm, repeat 5 mg IV push q 5 mins until target SBP reached (<120mmHg) or HR <55 bpm If HR increases by >15 bpm or is >90 bpm, add IV beta blocker
Hydralazine (IV)	
If BP persistently \geq 120 mmHg:
 
 ADD Hydralazine with a test dose: 5 mg IV bolus over 1 minute If SBP \geq 120 mmHg, repeat 5 mg IV bolus in 5 minutes If SBP still \geq120mmHg, give 10 mg IV bolus q 5 mins until target SBP reached. Increase to 20 mg bolus if required Maximum hydralazine dose = 240mg/24 hours
Glyceryl Trinitrate (Topical)	
If BP persistently \geq 120 mmHg:
 
 ADD topical glyceryl trinitrate (paste or patch) at a rate of 5-10 mg/24hour (\approx200-400 μg/hour). NB: also known as topical nitroglycerin
Continuous IV Infusions (requires ICU admission)	
If BP persistently \geq 120 mmHg:
 
 Phentolamine infusion 0.2-5 mg/minute If target still not reached, ADD infusion of hydralazine 50-150 μg/min OR glyceryl trinitrate 1-100 μg/Kg/min

MAINTENANCE therapy

BP Target	Maintenance of SBP 100-120 mmHg
Monitoring	
Once SBP is under target (confirmed by 4 readings 15 minutes apart):
 
 Record BP/HR q 30 minutes for 5 hours and then q 1 h for 18 h
IV treatment prn	
If SBP exceeds 120mmHg at any point:
 
 Give Phentolamine (5 mg) and/or hydralazine (10-20 mg) boluses. BP and HR should then be recorded 5 and 15 minutes later If SBP is 100-120mmHg, Phentolamine 5 mg (dose dependent on initial response) should be administered q 6 hours for the first 24 hours after symptom onset (total of 3 doses) If SBP \leq 100 mmHg or HR < 55 bpm, then cease treatment. If HR increases by >15 bpm or is >90 bpm, add IV beta blocker Note: phentolamine and hydralazine may be used together during the maintenance phase

Oral treatment

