Appendix 1D - BP protocol for centres with Hydralazine

Early intensive BP lowering group

TREATMENT PROTOCOL

INITIAL therapy

BP Target	SBP < 120 mmHg reached within 1 hour after randomisation
Monitoring	
 Continuous HR monitoring Record BP/HR q 5 mins during active treatment, then q 15 min for first hour, q 30 min for next 5 hours and then hourly to 24 h
Hydralazine (IV)	
 If BP persistently \geq 120 mmHg: ADD Hydralazine with a test dose: 5 mg IV bolus over 1 minute If SBP \geq 140mmHg, repeat 5 mg IV bolus in 5 minutes If SBP still \geq 120mmHg, give 10 mg IV bolus q 5 mins until target SBP reached Increase to 20 mg bolus if required Maximum hydralazine dose = 240mg
Metoprolol (IV)	
If BP persistently \geq 120 mmHg:
 
 ADD Metoprolol 5 mg IV bolus over 3-5 minutes, repeat 5mg bolus in 5 minutes x 2 if necessary but do NOT give if HR < 55bpm
Glyceryl Trinitrate (Topical)	
If BP persistently \geq 120 mmHg:
 
 ADD topical glyceryl trinitrate (paste or patch) at a rate of 5-10 mg/24hour (\approx200-400 μg/hour). NB: also known as topical nitroglycerin
Continuous IV Infusions (requires ICU admission)	
If BP persistently \geq 120 mmHg:
 
 Start infusion of hydralazine - 50-150 μg/min If target still not reached, ADD infusion of glyceryl trinitrate 1-100 μg/Kg/min OR start infusion of Nicardipine 5-15 mg/hour
MAINTENANCE therapy	
BP Target	Maintenance of SBP 100-120 mmHg
Monitoring	
Once SBP is under target (confirmed by 4 readings 15 minutes apart):
 
 Record BP/HR q 30 minutes for 5 hours and then q 1 h for 18 h.
IV treatment prn	
If SBP exceeds 120mmHg at any point:
 
 Give Hydralazine 10-20 mg boluses. BP and HR should then be recorded 5 and 15 minutes after each bolus If SBP is 100-120mmHg, give further Hydralazine 10-20 mg boluses (dependent on initial dose) q 6 hours for first 24 hours (total of 3 doses) If SBP \leq 100 mmHg or HR <55 bpm, then cease treatment
Oral treatment	Start treatment by 24 hours (use nasogastric if required)

- If not contraindicated and no other drug is specifically indicated, start combination therapy of ACEI + diuretics in addition to previous anti-hypertensives

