Appendix 1E - BP protocol for centres with Clevidipine

Early intensive BP lowering group

TREATMENT PROTOCOL

INITIAL therapy

BP Target	SBP < 120 mmHg reached within 1 hour after randomisation
Monitoring	
 Continuous HR monitoring Record BP/HR q 5 mins during active treatment, then q 15 min for first hour, q 30 min for next 5 hours and then hourly to 24 h
Clevidipine (IV) (requires ICU admission)	
If BP persistently ≥ 120mmHg:
 
 Initial Clevidipine dose: 2mg/h iv in first 1.5min If SBP≥ 120mmHg, add double dosage every 2-10min(4,8,16 until 32mg/h) Max dosage = 32mg/h
Hydralazine (IV)	
If BP persistently ≥ 120 mmHg:
 
 ADD Hydralazine with a test dose: 5 mg IV bolus over 1 minute If SBP ≥ 140mmHg, repeat 5 mg IV bolus in 5 minutes If SBP still ≥ 120mmHg, give 10 mg IV bolus q 5 mins until target SBP reached Increase to 20 mg bolus if required Maximum hydralazine dose = 240mg
Glyceryl Trinitrate (Topical)	
If BP persistently ≥ 120 mmHg:
 
 ADD topical glyceryl trinitrate (paste or patch) at a rate of 5-10 mg/24hour (≈ 200-400 μg/hour). NB: also known as topical nitroglycerin
Continuous IV Infusions (requires ICU admission)	
If BP persistently ≥ 120 mmHg:
 
 ADD infusion of hydralazine - 50-150 μg/min OR glyceryl trinitrate 1-100 μg/Kg/min
MAINTENANCE therapy	
BP Target	Maintenance of SBP 100-120 mmHg
Monitoring	Once SBP is under target (confirmed by 4 readings 15 minutes apart): 
 Record BP/HR q 30 minutes for 5 hours and then q 1 h for 18 h.
IV treatment prn	
If SBP exceeds 120mmHg at any point:
 
 DOUBLE the dose of Clevidipine every 2-10 minutes (4, 8, 16 and then maximum dose of 32 mg/hour) If SBP is 130-140mmHg, Keep the dose of Clevidipine If SBP < 120 mmHg or HR < 55 bpm, then HALVE the dose of Clevidipine every 2-10 minutes and then cease treatment If HR increases by >15 bpm or is >90 bpm, add IV beta blocker
Oral treatment	Start treatment by 24 hours (use nasogastric if required)

- If not contraindicated and no other drug is specifically indicated, start combination therapy of ACEI + diuretics in addition to previous anti-hypertensives

Note: Monoamine oxidase inhibitors are not recommended with this BP lowering agent and phosphodiesterase inhibitors must not be used with GTN.

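### In Appendices 1A and 1B the same reading can trigger both stopping BP lowering and adding an i.v. beta blocker, with no stated precedence; 1E has a related conflict

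*Protocol*

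**What the plan says.** Section 6.7 (Treatments Allocation) describes titration in the intensive group "with a systolic BP of 100 mmHg being the safety threshold for cessation of therapy". This is stated for the arm as a whole, not for one drug.

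The agent tables in Appendix 1 then give the working rules. Under maintenance therapy:

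- **1A (urapidil):** the bullet for SBP at or below the threshold ends "100 mmHg, cease therapy". The next bullet is "If HR increases by >15 bpm or is >90 bpm, add IV beta blocker".
- **1B (phentolamine):** the corresponding bullet ends "100 mmHg or HR < 55 bpm, then cease treatment", followed by the same heart-rate bullet.
- **1E (clevidipine):** the stopping bullet is "If SBP < 120 mmHg or HR < 55 bpm, then HALVE the dose of Clevidipine every 2-10 minutes and then cease treatment", again followed by the same heart-rate bullet.

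All three cells open with the lead-in "If SBP exceeds 120mmHg at any point". In 1A and 1B the heart-rate bullet also stands in the initial-therapy row for the main drug, with no lead-in above it.

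The protocol counts i.v. beta blockers as BP-lowering drugs in three places. Section 6.7 refers to "locally available i.v. agents (e.g. urapidil, hydralazine, metoprolol, clevipipine". Appendix 1D has the step "ADD Metoprolol 5 mg IV bolus over 3-5 minutes, repeat 5mg bolus in 5 minutes x 2 if necessary" for pressure that stays at 120 mmHg or more. Appendix 1F puts esmolol among its suggested i.v. drugs for lowering BP.

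**The concern.** One instruction withdraws BP-lowering treatment and the other adds a drug that this protocol uses to lower BP. If both can be live at the same reading, bedside staff have two written orders pointing in opposite directions, at the pressure the protocol itself names as the safety limit of the experimental arm.

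That limit matters to the conduct of the trial. Section 7.2.3 gives severe hypotensive events needing emergency treatment in the intensive group as an example of what would lead to amendment or early stopping. A literal reading of 1A or 1B could lead staff to add a BP-lowering drug at or below 100 mmHg, and two sites could follow the same table and act differently.

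**Working it through.** No formula applies. The check is whether the two triggers can both be true for one observation, table by table. The tables call for BP and HR to be recorded together, so both triggers are read from the same line of the chart.

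| Table (maintenance) | Stopping rule | Heart-rate rule | Readings that meet both |
|---|---|---|---|
| 1A | SBP ≤100 mmHg: cease | HR >90 bpm, or rise >15 bpm: add i.v. beta blocker | SBP ≤100 with HR >90 or rise >15 |
| 1B | SBP ≤100 mmHg or HR <55 bpm: cease | as 1A | SBP ≤100 with HR >90 or rise >15 |
| 1E | SBP <120 mmHg or HR <55 bpm: halve clevidipine, then cease | as 1A | SBP <120 with HR >90 or rise >15 |
| 1C | SBP ≤100 mmHg or HR <55 bpm: cease | none | none |
| 1D | SBP ≤100 mmHg or HR <55 bpm: cease | none | none |

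**Step 1: put readings in (1A and 1B).** At SBP 98 and HR 95, 98 ≤ 100 and 95 > 90, so both bullets apply. At SBP 98 with HR up from 70 to 88, the rise is 88 − 70 = 18 > 15, so both apply although HR is below 90. The HR <55 stop in 1B does not help, since it concerns slow rates.

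**Step 2: 1E.** Its table has no bullet that stops treatment at 100 mmHg. At SBP 100–119 with HR 95, staff are told to halve and then stop clevidipine and also to add a beta blocker. This lies within the table's own maintenance range of 100–120 mmHg. At 100 mmHg and below, the arm-wide threshold in section 6.7 also applies, but only from that section.

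**Step 3: does the lead-in settle it?** The lead-in restricts to SBP above 120 mmHg. It cannot govern every bullet, because others in the same cell apply at 100–120 and ≤100 mmHg (1A, 1B) or below 120 mmHg (1E). It could govern only those bullets that state no pressure of their own. The text does not say that it does.

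**Step 4: does any other text rank the two?** Section 6.7 allows treatment to be modified on clinical judgment and asks staff to avoid severe hypotension by checking for dehydration and giving fluids. Neither statement mentions the beta blocker or sets an order. No other section does so either.

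**The case against.** The strongest reply is the lead-in. The first bullet in the 1A and 1B cells gives the main drug without stating a pressure, so it must take its condition from the lead-in. The heart-rate bullet also states no pressure, so it may take the same condition and apply only above 120 mmHg. On that reading there is no clash at 100 mmHg in the maintenance cell. Indentation may have been lost in the PDF text, so a layout cue cannot be excluded. This reading is possible, but it is unstated. The heart-rate bullet comes after two bullets that set the lead-in aside, and the same bullet stands in the initial-therapy rows of 1A and 1B with no lead-in. Those rows contain no stopping bullet, so the direct pairing is confined to maintenance.

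The second reply is that if beta blockers are BP-lowering agents here, the 6.7 threshold already covers them, and clinical judgment does the rest. This softens the practical effect. It does not order the instructions. The same section, under discontinuation of allocated management, restricts deviation to withdrawal of consent before allowing modification in the patient's interest, so discretion is not a clear tie-break.

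Four stronger inferences are tempting and are not supported:

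- **That 1E repeats the 1A/1B conflict.** It has no stopping bullet at 100 mmHg. Reducing one drug for pressure while adding another for heart rate is also less plainly contradictory than stopping and adding.
- **That 1D shows a condition was left out elsewhere.** Its metoprolol step is an escalation step for persistently raised pressure, not a tachycardia rule. It shows only how the protocol classes the drug.
- **That a number of affected patients can be given.** The documents report neither how often both triggers coincide nor how patients divide among the agent tables.
- **That the conflict distorts the estimated treatment effect.** The trial compares BP strategies with flexible drug choice, and nothing in the SAP turns on this rule.

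**Conclusion.** The point holds as an unresolved conflict between written instructions. It is direct in the maintenance cells of 1A and 1B, and takes a different, weaker form in 1E. That is three of the five agent-specific tables (1A to 1E), two in the direct form, and 1A and 1B are the two headed for use in China. The conflict covers SBP ≤100 mmHg in 1A and 1B, and SBP <120 mmHg in 1E, with HR above 90 bpm or a rise of more than 15 bpm.

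Two assumptions carry the conclusion: that the heart-rate bullet is not silently limited by the lead-in, and that stopping therapy is meant to include BP-lowering drugs in general. If the sponsor intended the lead-in to limit the heart-rate bullet, the conflict disappears in substance, but the tables still need to say so. The importance lies in participant safety at the arm's own threshold. No frequency can be given, and no endpoint, sample size or analysis is affected.

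**What to change.** The sponsor's clinical team should reconcile section 6.7 with Appendices 1A, 1B and 1E and state three things:

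1. whether the instruction to cease covers the i.v. beta blocker;
2. at which SBP values the heart-rate bullet is meant to apply, in both the maintenance cells and the initial-therapy rows where it appears;
3. which instruction governs when both are met.

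The content is for the clinical team, and no clinical rule is proposed here.

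The cost is a clarifying sentence in each of three tables, a matching line in 6.7 if needed, and a notice to sites. If it is issued as a protocol amendment, section 6.4.1 already assigns reporting to the ethics committees to the site investigators. Data collection and the SAP need no change.

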Appendix 1C - BP protocol for centres with Labetalol

Early intensive BP lowering group

TREATMENT PROTOCOL

INITIAL therapy

BP Target	SBP < 120 mmHg reached within 1 hour after randomisation
Monitoring	
 Continuous HR monitoring Record BP/HR q 5 mins during active treatment, then q 15 min for first hour, q 30 min for next 5 hours and then hourly to 24 h
Labetalol (IV)	
 If SBP \geq 120 mmHg and HR >55 bpm, repeat 20 mg IV push q 5 mins until target SBP reached (< 120 mmHg) or HR <55 bpm; increase to 40 mg bolus if required Maximum labetalol dose: 300 mg / 24 hours
Hydralazine (IV)	
If BP persistently \geq 120 mmHg:
 
 ADD Hydralazine with a test dose: 5 mg IV bolus over 1 minute If SBP \geq 120 mmHg, repeat 5 mg IV bolus in 5 minutes If SBP still \geq 120 mmHg, give 10 mg IV bolus q 5 mins until target SBP reached. Increase to 20 mg bolus if required Maximum hydralazine dose = 240mg/24 hours
Glyceryl Trinitrate (Topical)	
If BP persistently \geq 120 mmHg:
 
 ADD topical glyceryl trinitrate (paste or patch) at a rate of 5-10 mg/24hour (\approx200-400 μg/hour). NB: also known as topical nitroglycerin
Continuous IV Infusions (requires ICU admission)	
If BP persistently \geq 120 mmHg:
 
 Labetalol infusion 2-8 mg/min to a maximum of 300 mg/24 hours (consider this if response to labetalol boluses is adequate but brief) If target still not reached, ADD infusion of hydralazine 50-150 μg/min OR glyceryl trinitrate 1-100 μg/Kg/min OR start infusion of Nicardipine 5-15 mg/hour

MAINTENANCE therapy

BP Target	Maintenance of SBP 100-120 mmHg
Monitoring	Once SBP is under target (confirmed by 4 readings 15 minutes apart): 
 Record BP/HR q 30 minutes for 5 hours and then q 1 h for 18 h.
IV treatment prn	
If SBP exceeds 120 mmHg at any point:
 
 Give Labetalol (20-40 mg) and/or hydralazine (10-20 mg) boluses. BP and HR should then be recorded 5 and 15 minutes later If SBP is 100-120 mmHg, Labetalol 10-40 mg (dose dependent on initial response) should be administered q 6 hours for the first 24 hours after symptom onset (total of 3 doses) If SBP \leq 100 mmHg or HR < 55 bpm, then cease treatment Maximum labetalol dose: 300 mg/24 hours

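### Appendix 1A (urapidil) is the only one of the five maintenance blocks with no stop or step-down at a heart rate below 55 bpm

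*Protocol*

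**What the plan says.** Appendix 1A has an initial phase and a maintenance phase.

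- **Initial phase, urapidil bolus row.** Boluses depend on HR. The condition is SBP at or above 120 "mmHg and HR >55 bpm, repeat 10-25 mg IV bolus q5 mins until target SBP reached (<120mmHg) or HR <55 bpm".
- **Initial phase, infusion row.** If SBP stays at or above 120 mmHg, urapidil 5-30 mg/hour may be infused. No HR condition is attached.
- **Maintenance, SBP above 120 mmHg.** "Give Urapidil (10-25 mg) and/or hydralazine (10-20 mg) boluses". No HR condition.
- **Maintenance, SBP 100-120 mmHg.** "If SBP is 100-120mmHg, Urapidil 10-25 mg (dose dependent on initial response) should be administered q 6 hours". The line limits this to the first 24 hours after symptom onset and to three doses. No HR condition.
- **Maintenance, stop rule.** At or below "100 mmHg, cease therapy". No HR term.
- **Maintenance, the only action triggered by HR.** An i.v. beta blocker is added if HR rises by more than 15 bpm or exceeds 90 bpm.

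The corresponding stop rule in Appendix 1B maintenance reads "100 mmHg or HR < 55 bpm, then cease treatment", again at or below that pressure. Protocol section 6.7 gives one cessation threshold for the intensive group, an SBP of 100 mmHg, and no HR threshold.

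**The concern.** Appendices 1A to 1E are built on a common template, and staff at a urapidil centre will work from 1A at the bedside. Its maintenance block tells them what to do when HR is high but not when it is low. In the 100-120 mmHg band the wording is directive: the dose should be given, whatever the HR. Above 120 mmHg urapidil is one of two options, again whatever the HR. At a centre using 1B, 1C or 1D, a patient with HR below 55 bpm would have treatment ceased.

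What is at stake is consistent safety instructions within the experimental arm. The analysis is not affected.

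**Working it through.** The protocol gives no figure to reproduce. The check sets the appendices side by side, with some arithmetic on the limits of the scheduled dose and the monitoring.

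**Step 1. HR limits by appendix.**

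| Appendix | Main agent | HR limit on main agent's initial boluses or dosing | Action in maintenance at HR <55 |
|---|---|---|---|
| 1A | urapidil | yes, bolus row only | none |
| 1B | phentolamine | yes ("repeat 5 mg IV push q 5 mins until target SBP reached (<120mmHg) or HR <55 bpm") | cease |
| 1C | labetalol | yes ("repeat 20 mg IV push q 5 mins until target SBP reached (< 120 mmHg) or HR <55 bpm") | cease |
| 1D | hydralazine | no | cease |
| 1E | clevidipine | no | halve, then cease |
| 1F | additional drug list | no | no maintenance block |

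Six i.v. appendices have five maintenance blocks. Four of the five (1B to 1E) act on low HR, and the exception is 1A. Three appendices (1A, 1B, 1C) put an HR limit on the main agent's initial boluses. Two of these (1B, 1C) also have an HR stop in maintenance, and 1A does not.

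**Step 2. Closest comparator.** The 1A and 1B maintenance blocks match almost line for line: the as-needed bolus with hydralazine as partner, the six-hourly dose at 100-120 mmHg, the beta-blocker instruction for high HR, and the note on combined use. Apart from drug and dose, the substantive difference is that 1B's stop rule has the HR limb and 1A's does not. 1B pairs its instruction to add a rate-lowering drug with a low-HR stop, and 1A gives the same instruction without one.

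**Step 3. What 1A's own initial phase shows.** Above 120 mmHg, it withholds the five-minute urapidil bolus at HR below 55, so the authors did apply this limit to urapidil boluses. It does not withhold the infusion. In the 100-120 mmHg band it is no comparator, because its boluses stop once SBP is below 120.

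**Step 4. Reach of the scheduled dose.** With a cap of three doses, the total is 3 × 10 = 30 mg to 3 × 25 = 75 mg. The window closes 24 hours after onset. If a patient is randomised t hours after onset, 24 − t hours remain. The text does not say when the first dose falls. I assume a range from immediately to six hours after randomisation:

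- t = 6: 18 hours remain, 18/6 = 3, so 3 doses (the cap).
- t = 12: 12 hours remain, 12/6 = 2, so 2 to 3 doses.
- t = 18: 6 hours remain, 6/6 = 1, so 1 to 2 doses.
- t above 24: none.

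Section 6.3 admits thrombectomy up to 24 hours after onset and qualifying SBP up to 3 hours after recanalisation, so the last case can occur. The as-needed bolus has no such time limit.

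**Step 5. Monitoring.** Once the target is confirmed, the instruction is "Record BP/HR q 30 minutes for 5 hours and then q 1 h for 18 h", which is 5 + 18 = 23 hours. Section 6.7 holds the target for 72 hours. HR is also recorded 5 and 15 minutes after as-needed boluses. Continuous HR monitoring is listed under initial therapy, and the maintenance block neither repeats nor ends it.

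**Step 6. Search for a rule elsewhere.** Neither section 6.7 nor any other part of the protocol or SAP states a low-HR stop covering urapidil maintenance.

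**The case against.** The best case against the point is that the difference may be deliberate. HR could be meant to gate rapid five-minute titration, and neither infusion nor spaced dosing. 1A's ungated infusion row fits that reading. The comparators are also uneven. 1D and 1E have no HR limit on their main agent initially but gain one in maintenance. 1E keeps the clevidipine dose at 130-140 mmHg, which does not fit its own 100-120 target. Blocks edited this unevenly are imperfect evidence that 1A is the one in error. This stands as a reason for modest language. The match with 1B, and the HR limit on 1A's own initial boluses, still make an oversight the likelier explanation.

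The safeguards are real: continuous HR monitoring under initial therapy, scheduled recording, hydralazine alone as an option above 120 mmHg, exclusion of patients with contraindications to the agents (6.3), and freedom to modify treatment or a duty to change it in the patient's interest (6.7). They reduce the risk, but none states a threshold for action, and exclusion at entry does not cover bradycardia that develops on treatment.

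A reader might also infer three stronger things that the documents do not support:

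- **That 1A's initial phase withholds all urapidil at HR below 55, so the appendix contradicts itself.** Only the bolus row has the limit.
- **That the omission exposes patients to a known urapidil bradycardia hazard.** Neither document says that urapidil slows the heart or is unsafe below 55 bpm.
- **That scheduled dosing without an HR check runs through the 72-hour target period.** It ends after three doses or 24 hours from onset.

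**Conclusion.** The point holds as a matter of text. 1A is the one maintenance block of five without a low-HR stop or step-down, and no other provision supplies one. Two instructions are affected: the as-needed urapidil bolus above 120 mmHg, which is permitted at any HR, and the six-hourly 10-25 mg dose at 100-120 mmHg, which is directed at any HR within its dose and time limits.

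This is a minor safety-consistency correction in the experimental arm. Endpoints, power and analysis are unaffected. The conclusion rests on comparing the appendices, and the judgement that the gap is unintended is an inference. The documents give neither the frequency of HR below 55 bpm nor the share of centres using 1A, so the number of patients affected cannot be estimated.

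**What to change.** Add one clause to the 1A maintenance block: *withhold urapidil boluses, as-needed or six-hourly, if HR <55 bpm.* This mirrors the HR limit in 1A's initial bolus row and leaves hydralazine available above 120 mmHg.

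If the sponsor's clinicians prefer uniformity, the alternative is the combined SBP-or-HR stop used in 1B to 1D. Its drawback is that it would also stop hydralazine in a patient still above target. The clinicians should confirm the 55 bpm threshold for urapidil or, if no limit is intended, state the reason in 1A.

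The cost is the clause, a site letter and a minor amendment. Under section 6.4.1 amendments go to each site's review board through the site investigator. The protocol plans 80-100 hospitals in China and the SAP reports about 60, so the administrative step is not nothing, though the change is small. Urapidil would occasionally be withheld from a bradycardic patient. Sample size, visits and analysis do not change.
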